## Memorial Sloan-Kettering Cancer Center IRB Protocol

IRB#: 09-159A(10)

**11.3** GM-CSF: Common side-effects include bone pain, flushing, local reaction at site of injection, leukopenia shortly after injection, and decrease in platelet count. Rare side-effects (predominantly in adults) include allergic reactions, weight gain, pleural or pericardial effusion, pericardial embolism, thrombosis, and difficulty breathing after first injection.

**11.4** Isotretinoin: Dry skin, dry mouth, cheilitis, dry eyes, hypercalcemia, pseudotumor cerebri, rash, muscle or bone pain, fatigue, headache, cholesterol, nausea and vomiting, changes in skin color, upset stomach, dizziness, low red and white blood cells, retinoic acid syndrome, hepatotoxicity, teratogenic effect on fetus, depression, suicidal ideation.

## 12.0 CRITERIA FOR THERAPEUTIC RESPONSE/OUTCOME ASSESSMENT

**12.1** Response duration is calculated from first day of treatment with 3F8.

**12.2** Patients are considered a treatment failure if progressive disease develops.

**12.3** Disease status is defined by the International NB Response Criteria.

- Complete response/remission (CR): no evidence of disease by imaging studies and standard BM histology (section 8.4).
- Very good partial response/remission (VGPR): >90% decrease in all disease markers, except bone scan unchanged or improved; BM must be free of disease by histology and by scintigraphic studies.
- Partial response/remission: >50% decrease in all disease markers, except bone scan unchanged or improved;  $\leq 1$  positive BM site; MIBG scan must be negative or improved in all abnormal sites.
- Minor response: >50% decrease in  $\geq 1$  but not all disease markers; MIBG scan must be negative or improved in at least one site.
- No response: <50% decrease in all tumor markers, no change in MIBG scan.
- Progressive disease (PD): new lesion, or >25 % increase in any disease marker.

**12.4** All patients who fulfill the eligibility requirements and receive a first dose of 3F8 will be included in the analysis.

Amended: 02/24/15

## Memorial Sloan-Kettering Cancer Center IRB Protocol

IRB#: 09-159A(10)

### 13.0 CRITERIA FOR REMOVAL FROM STUDY

**13.1** PD any time after cycle 1. However, if a patient develops recurrent disease that can be completely eliminated surgically or eliminated by other means, that patient may remain on study at the discretion of the Principal Investigator as long as the patient does not receive systemic therapy and the recurrence is promptly eliminated.

**13.2** Life-threatening grade 4 toxicity clearly attributable to 3F8.

**13.3** The investigators will make every reasonable effort to keep each patient in the study until all planned treatments and assessments have been performed. The investigators may discontinue study drug treatment for the following reasons:

- **Adverse events**, including unacceptable toxicity or exacerbation of underlying disease, associated with study drug administration and necessitating discontinuation of treatment. Patients who are removed from the study due to adverse events will be treated and followed according to established, acceptable medical practice. All pertinent information concerning the outcome of such treatment will be entered in the Case Report Form or on the Serious Event Report, as applicable.
- **Withdrawal of consent.** The patient's desire to withdraw from the study may occur at any time. The investigator should carefully consider whether the patient's withdrawal of consent is due to an adverse event, and if so, record the adverse event as the reason for withdrawal.
- **Withdrawal by the physician** for clinical reasons not related to study drug treatment, for example, clinical need to administer a concomitant medication that is excluded by the protocol, in the absence of an adverse event.
- **Violation of the study protocol**, including failure to return for required treatments or assessments. Patients who fail to return for treatments will be withdrawn from the study if more than 4 scheduled doses are missed

**13.4** Patients will not be removed from study in order to receive radiotherapy.

**13.5** Patients removed from the study will not be replaced. Every effort will be made to follow these patients, with extent-of-disease evaluations performed at least every 3 months through ≥2 years from study enrollment.

Amended: 02/24/15

## Memorial Sloan-Kettering Cancer Center IRB Protocol

IRB#: 09-159A(10)

### 14.0 BIOSTATISTICS

The objective of this phase II trial is to assess the anti-NB activity of high-dose 3F8 plus GM-CSF in patients in first CR/VGPR from high-risk NB after conventional therapy. The 3F8 dosing is four fold greater than the standard 3F8 dosage used in prior phase II studies.

In A(8), treatment was changed to use standard dose 3F8 ( $20 \text{ mg/m}^2/\text{day}$ ) for all cycles instead of high-dose 3F8 for cycles 1 and 2. Patients treated as such are evaluable for toxicity only.

#### 14.1 Primary Endpoint

The primary endpoint is two-year relapse-free survival (RFS).

#### 14.2 Sample Size

We will use a Simon's two-stage design. The type I error rate is set as 0.1 and the type II error rate as 0.1.

In the predecessor trial (IRB 03-077: 3F8 at standard dosage of  $100 \text{ mg/m}^2/\text{cycle}$ , (administered initially as  $10 \text{ mg/m}^2/\text{day} \times 10$  days per cycle, and subsequently as  $20 \text{ mg/m}^2/\text{day} \times 5$  days per cycle) combined with GM-CSF, plus 13-cis-retinoic acid, the 56 patients treated in CR/VGPR after conventional therapy achieved 70% two-year RFS. By taking into account of the small sample variation, we will consider a two-year RFS rate 0.64 as not promising and 0.80 as promising with the new treatment. Twenty-two patients will be accrued initially, and if there are less than 15 RFSs, further accrual to the protocol will be stopped and the new treatment will be declared ineffective in this protocol. If there are at least 15 RFSs, then an additional 36 patients will be accrued for a total of 58. If at least 42 RFSs out of 58 patients, the protocol would be considered to have a positive result and the new treatment would be considered worthy of further testing in this patient population. The probability of stopping the study earlier is 57% under the null hypothesis.

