### 4.0 OVERVIEW OF STUDY DESIGN/INTERVENTION

#### 4.1 Design

This phase II, open-label, single arm trial assesses the anti-NB activity of high-dose 3F8 (80 mg/m^2/day), which is used in cycles 1-2, with return to standard 3F8 dosage (20 mg/m^2/day) in subsequent cycles. Clinical results will be compared to those in the predecessor trials which used only the standard 3F8 dosage.

Starting with A(8), patients no longer receive high dose 3F8 but receive only standard dose 3F8 (20mg/m^2/day) for all cycles.

The patients are in 1st complete/very good partial remission (CR/VGPR) after conventional therapy, with no evidence of NB by standard studies, but are at high risk for relapse.

Real-time quantitative RT-PCR will be used to assess MRD in BM. 13-*cis*-retinoic acid is started after cycle 2.

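### Section 14.2 was not updated after A(8): the number of high-dose patients evaluable for two-year RFS is not given, and the only boundary, 42 of 58, meets its stated error rates only at 58

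*Combined protocol and SAP*

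**What the plan says.** Section 14.2 sets out a Simon two-stage design for two-year relapse-free survival (RFS).

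- Error rates: "The type I error rate is set as 0.1 and the type II error rate as 0.1".
- Hypotheses: "we will consider a two-year RFS rate 0.64 as not promising and 0.80 as promising with the new treatment".
- Stage 1: "Twenty-two patients will be accrued initially, and if there are less than 15 RFSs, further accrual to the protocol will be stopped".
- Stage 2: "an additional 36 patients will be accrued for a total of 58".
- Final rule: "If at least 42 RFSs out of 58 patients, the protocol would be considered to have a positive result".
- Early stopping: "The probability of stopping the study earlier is 57% under the null hypothesis".

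Amendment A(8) changed who receives the treatment under test. Section 4.1 says: "Starting with A(8), patients no longer receive high dose 3F8 but receive only standard dose 3F8". The footnote to the schema in 4.2 and the schedules in 9.1 and 9.2 limit the high dose to patients who came on under A(0) to A(7). Section 14.0, which still names activity of the high dose as the trial objective, says of those given standard dose in all cycles: "Patients treated as such are evaluable for toxicity only".

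Section 12.4 has no matching exception. It keeps in the analysis every eligible patient who receives a first dose of 3F8. Section 13.5 says that patients removed from the study are not replaced.

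**The concern.** Taken together, 4.1, 4.2 and 14.0 close the RFS-evaluable sample at the number N of high-dose patients treated under A(0) to A(7). Section 14.2 still reads as if accrual to 58 were open. The documents do not give N, do not say whether stage 1 was passed, and give no rule for any number other than 58.

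This is the primary decision rule of a single-arm trial. If N is not 58, the analyst must choose after the fact between keeping 42, keeping the proportion 42/58, recomputing the boundary, or filling up to 58 with standard-dose patients. Section 14.0 rules out the last option, but 12.4 read alone would permit it.

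These choices can give opposite answers. Suppose N were 40 and 29 patients were relapse-free. The proportion gives 42/58 × 40 = 28.97, so 29 passes. The smallest boundary with type I error at most 0.10 is 30, so 29 fails. A cut-off of 42 could never be reached.

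**Working it through.** **Inputs (all from 14.2).** p0 = 0.64, p1 = 0.80; stage 1 n = 22, continue with 15 or more; total 58, positive with 42 or more; type I and type II error limits 0.10 each.

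**Formula.** For a total of N and a final cut-off r, with the stage 1 rule unchanged,

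P(positive | p) = Σ over x = 15 to 22 of Bin(x; 22, p) × P(Bin(N − 22, p) ≥ r − x).

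Type I error (alpha) is this sum at p = 0.64, and power is the sum at p = 0.80.

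**Step 1: reproduce the plan (N = 58, r = 42).** Under p0, P(14 or fewer of 22) = 0.566, which matches the stated 57%. Alpha is 0.099 and power is 0.906. The design is correct as calculated.

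**Step 2: vary N.** The documents do not give N, so it is an assumption here and a range is shown. Three ways of handling N other than 58 are compared: keep 42; keep the proportion 42/58 = 72.4%, rounded up; or reset to the smallest cut-off with alpha at most 0.10.

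| N | Keep 42: alpha / power | Proportion: cut-off, alpha | Reset: cut-off, alpha / power |
|---|---|---|---|
| 26 | cannot be reached | 19, 0.226 | 21, 0.053 / 0.58 |
| 30 | cannot be reached | 22, 0.187 | 24, 0.047 / 0.61 |
| 31 | cannot be reached | 23, 0.157 | 24, 0.082 / 0.73 |
| 40 | cannot be reached | 29, 0.155 | 30, 0.093 / 0.83 |
| 46 | <0.001 / 0.03 | 34, 0.097 | 34, 0.097 / 0.86 |
| 50 | 0.002 / 0.31 | 37, 0.083 | 37, 0.083 / 0.87 |
| 54 | 0.021 / 0.72 | 40, 0.072 | 40, 0.072 / 0.87 |
| 55 | 0.034 / 0.79 | 40, 0.099 | 40, 0.099 / 0.90 |
| 56 | 0.051 / 0.84 | 41, 0.085 | 41, 0.085 / 0.89 |
| 57 | 0.073 / 0.88 | 42, 0.073 | 42, 0.073 / 0.88 |
| 58 | 0.099 / 0.906 | 42, 0.099 | 42, 0.099 / 0.906 |
| 59 | 0.129 / 0.92 | 43, 0.086 | 43, 0.086 / 0.90 |
| 60 | 0.162 / 0.93 | 44, 0.074 | 44, 0.074 / 0.89 |

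Among these N, a cut-off of 42 meets both 0.10 limits only at 58. One patient fewer takes power below 0.90, and one more takes alpha above 0.10. From 46 to 60, at the values tabulated, the proportion and the reset boundary coincide. They part at 40 and below.

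**Step 3: can N be inferred?** Section 14.3 expects 10 to 15 patients a year and completion in 3 to 4 years. That gives 3 × 10 = 30 to 4 × 15 = 60 patients. Reaching 58 would take 58/15 = 3.9 to 58/10 = 5.8 years. Section 7.0 cites 46 patients a year on the predecessor protocol. These figures are compatible with N below, at or above 58, and the text does not say how long high-dose enrolment ran.

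**The case against.** The strongest reply is that no shortfall has been shown. Making later patients toxicity-only is just what one would write if the high-dose cohort were already full, and in that case 14.2 is right as it stands. This reply stands, and it makes the point conditional.

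A reader might go further and infer that the rule has no valid form unless exactly 58 high-dose patients were treated, or that every way of applying it fails. The documents and the arithmetic do not support either reading:

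- Below 58, a cut-off of 42 amounts to counting the missing patients as failures. Alpha stays at or below 0.073. The cost is power, and it is modest close to 58 (0.88 at 57, 0.84 at 56).
- Keeping the proportion does not always inflate alpha. It does at N = 26, 30 and 40, but not at 46, 50 or 55.
- Above 58, the rule could be applied to the first 58 patients, although 14.2 does not say so.
- The stage 1 rule does not depend on reaching 58.
- Section 14.0 already excludes standard-dose patients from the efficacy count. The risk that they are counted arises only from 12.4.

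What the reply leaves standing is that neither N nor a rule for another N is written down, so a reader cannot tell which row of the table applies.

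**Conclusion.** The concern holds in a limited form. A(8) closed the RFS-evaluable sample, and 14.2 was not adapted. Its stated error rates can be relied on only if N is 58, and the documents neither confirm nor contradict that.

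The consequence ranges from nothing (N = 58), through a small loss of power (N = 56 or 57), to a rule that has little or no chance of a positive result (power 0.03 at 46, zero below 42). If more than 58 were counted against 42, a positive result would be too easy.

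The figures assume that the stage 1 rule was applied as written, that each patient's two-year status is known, and the plan's own p0 and p1. It should not be concluded that the trial fell short of 58 or that its result would be invalid.

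**What to change.** In 14.2, state the number of high-dose patients enrolled under A(0) to A(7) who are evaluable for two-year RFS.

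- **If it is 58**, say so and leave the rule unchanged.
- **If it is not 58**, replace 42 of 58 with the smallest boundary that holds alpha at or below 0.10 for that N, and state its actual alpha and power. Examples are 24 of 31 (0.082, 0.73), 30 of 40 (0.093, 0.83), 37 of 50 (0.083, 0.87) and 40 of 55 (0.099, 0.90). At 57 the boundary remains 42, and only the stated power changes.
- Fix the boundary before two-year outcomes are tabulated.
- State that standard-dose patients enrolled from A(8) do not count towards the 58, and reconcile 12.4 with 14.0 accordingly.

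The cost is about one paragraph in 14.2 and a clause in 12.4, with no extra patients. The downside is that the stated power will be less favourable if N is below 58.

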#### 14.3 Accrual Rate

We expect to accrue 10-15 patients per year. This trial can be completed within 3-4 years. The accrual will continue after the first stage of the study, and the two-stage design is used to guard against many early recurrences.

Amended: 02/24/15

## Memorial Sloan-Kettering Cancer Center IRB Protocol

IRB#: 09-159A(10)

### 14.4 Secondary Endpoint

The association between histologic examination and real time RT-PCR regarding BM status will be assessed by the Wilcoxon statistic. The clinical significance (relapse-free survival) of histologic results and real time RT-PCR findings will be assessed by log-rank test and Cox regression model.

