### 1.0 PROTOCOL SUMMARY AND/OR SCHEMA

This phase II study of the anti-GD2 murine IgG3 monoclonal antibody 3F8 combined with granulocyte-macrophage colony stimulating factor (GM-CSF) will assess relapse-free survival in patients who are in first complete/very good partial remission (CR/VGPR) but are at very high risk of relapse of neuroblastoma. The high-dose 3F8 usage is four fold greater than the standard 3F8 dosage used in prior phase II studies. 13-*cis*-Retinoic Acid will be used in this protocol after patients are evaluated for response to 3F8/GM-CSF. We will apply real-time quantitative RT-PCR methodology targeting GD2 synthase mRNA for monitoring response in bone marrow; we will test the hypothesis that early bone marrow response has prognostic importance.

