#### Secondary Objectives

- Apply real-time quantitative RT-PCR to test the hypothesis that the minimal residual disease content of bone marrow after the first treatments with 3F8/GM-CSF has significant prognostic impact on relapse-free survival.
- Monitor safety of the high-dose antibody treatment, to assure no side-effects or noxious sequelae develop or emerge that were not seen in the prior phase I study.

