## 8.0 PRETREATMENT EVALUATION

Pretreatment evaluations should be completed within 30 days of start of treatment. Refer to Table 1.

8.1 Complete history and physical examination.

8.2 Complete blood count, serum creatinine, blood urea nitrogen, serum aspartate aminotransferase, serum alanine aminotransferase, and serum total bilirubin

8.3 Echocardiogram.

8.4 Complete extent-of-disease evaluation.

8.4.1 Urine catecholamine levels - optional.

8.4.2 BM aspirates from bilateral anterior and bilateral posterior iliac crests, and biopsies from any two separate sites. The specimens are studied by:

- Standard histochemical methods for the presence of tumor cells.
- Immunocytology using a panel of monoclonal antibodies that react with antigens associated with NB (to [name] lab).

Amended: 02/24/15

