## Memorial Sloan-Kettering Cancer Center IRB Protocol

IRB#: 09-159A(10)

- RT-PCR quantitation of tumor cells (to [name] lab)

8.4.3 CT or MRI of primary tumor site, plus other suspected sites of tumor.

8.4.4 Scintigraphic studies (MIBG scan or PET scan).

8.5 Biologic (blood) studies for phenotypes of leukocytes, and for DNA to do HLA and KIR typing, FcR2A and FcR3A polymorphism (to be drawn prior to treatment).

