## Memorial Sloan-Kettering Cancer Center IRB Protocol

IRB#: 09-159A(10)

**10.6** Liver and kidney function blood tests on day 0 and +4 of each cycle.

**10.7** Assessment of response is the same as in prior studies, including the predecessor 3F8/GM-CSF (IRB 03-077) protocol: BM studies (8.4.2) after cycle 2 and complete extent-of-disease evaluation (section 8.4) after cycle 4 of 3F8/GM-CSF and at least every 3 months through 2 years. BM studies are repeated in conjunction with MIBG or PET scan (section 8.4.4) through 2 years in patients with history of BM or cortical bone involvement, but are repeated ~every 6 months in other patients (e.g., patients who were stage 4 by virtue of metastases in distant lymph nodes, patients with *MYCN*-amplified stage 4S lacking BM involvement, or patients with *MYCN*-amplified stage 2 or stage 3).

**10.8** Pregnancy screen (females of child-bearing age) before starting *cis*-retinoic acid.

**10.9** Blood to study minimal residual disease (to [name] lab)

**10.10** Patients receiving 80 mg/m^2 of 3F8 will be monitored for their blood pressure for at least 2 days after 3F8 until a normal blood pressure has been assured. Not applicable starting with A(8)

Table 1. PRETREATMENT AND DURING THE STUDY EVALUATION

WHAT?	WHEN?
Complete history and physical examination.	Pretreatment evaluation
Complete blood count	1. Pretreatment evaluation 2. On day 0 (i.e. Monday) and +3 (i.e. Thursday).
Liver and kidney function blood tests	1. Pretreatment 2. On day 0 (i.e. Monday) and +4 (i.e. Friday)
Blood for studies of DNA to do HLA and KIR typing, FcR2A and FcR3A polymorphism (to [name] lab)	Pretreatment or on Cycle 1 Day 0 prior to 3F8.
Blood for studies of phenotypes of leukocytes (to [name] lab)	Day 0 (i.e. Monday) prior to treatment and Day 4 (i.e. Friday), cycles 1 and 2
Blood (2-5 ml) for 3F8 levels (to [name] lab)	1. Pre 3F8 infusion day 0 (i.e. Monday), cycles 1 and 2 2. Post 3F8 infusion day 4 (i.e. Friday), cycles 1 and 2
Blood for minimal residual disease studies (to [name] lab)	1. Drawn with post cycle 2 bone marrow studies 2. Drawn with bone marrows during first work-up (~3 months from start of study)
C3, CH50	On day 0 and +4 (i.e. Monday and Friday), cycles 1 and 2.
HAMA (Red Top Tube) (to [name] lab)	~Every 1-2 months while on study.

Amended: 02/24/15

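### Section 14.4 tests the post-cycle-2 marrow result against RFS without a landmark, so one specimen can supply both predictor and relapse and make a non-prognostic RT-PCR result look prognostic

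*Combined protocol and SAP*

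**What the plan says.** All references are to the combined protocol.

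- **Hypothesis.** Section 2.0 sets out to test whether the "minimal residual disease content of bone marrow after the first treatments with 3F8/GM-CSF has significant prognostic impact on relapse-free survival".
- **Analysis.** Section 14.4 says of the association with RFS that "real time RT-PCR findings will be assessed by log-rank test and Cox regression model". Histologic results are to be tested against RFS in the same way. No landmark, delayed entry, time-varying covariate or rule for early relapses is given.
- **Predictor visit.** Section 10.7, under assessment of response, schedules "BM studies (8.4.2) after cycle 2 and complete extent-of-disease evaluation (section 8.4) after cycle 4 of 3F8/GM-CSF".
- **Two readings of one marrow.** Section 8.4.2 sends the specimens for "Standard histochemical methods for the presence of tumor cells" and for "RT-PCR quantitation of tumor cells".
- **Clock.** Section 12.1: "Response duration is calculated from first day of treatment with 3F8". Neither 14.1 nor 14.4 gives a separate origin for RFS.
- **Event and analysis set.** Progressive disease is treatment failure (12.2). CR and VGPR both require a histologically clear marrow (12.3), and patients enter in first CR/VGPR (6.1.3). Every eligible patient with a first 3F8 dose is analysed (12.4). Progression at any time after cycle 1 is a reason for removal from study (13.1).

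**The concern.** Because entry marrow is histologically clear, tumour seen by histology after cycle 2 is new disease and so an RFS event. Section 3.4 says that histology underestimates marrow involvement and puts the RT-PCR detection limit at 1 in 10^5 to 1 in 10^7 cells, so that same specimen is very likely RT-PCR positive. On a clock that starts at first 3F8, such a patient enters the log-rank or Cox analysis as marker-positive with an event at the moment the marker was measured. That association arises even if RT-PCR says nothing about later relapse in patients still in remission.

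For histology the problem is sharper. If the post-cycle-2 reading is the one tested, a positive result is itself the relapse.

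A patient who progresses before that marrow has no marker value, and no rule says how to handle this.

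Section 3.8 hopes that the marker will help identify patients unlikely to benefit from continuing an adjuvant therapy, and inform later treatment programs. That use needs evidence that residual disease in a patient still in remission predicts later relapse. Relapses found on the marker specimen cannot provide it.

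**Working it through.** **1. The plan's own figures.** No figure is stated for the RT-PCR analysis. The design inputs borrowed here (58 patients, two-year RFS 0.64 and 0.80) come from 14.2, and that design reproduces by exact binomial calculation:

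- Early stopping at 0.64: P(X ≤ 14 | n = 22) = 0.566 (stated 57%).
- Success probability: sum over x ≥ 15 of P(X = x | 22) × P(Y ≥ 42 − x | 36) = 0.099 at 0.64 (target 0.1) and 0.906 at 0.80 (target 0.9).

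**2. When the marker marrow falls.** From 4.2, cycle 1 is days 0–4 and breaks are 2–4 weeks. Cycle 2 starts on day 4 + 14 = 18 to 4 + 28 = 32 and ends on day 22 to 36. Cycle 3 starts on day 36 to 64. I assume the marrow is taken at 1.5 months, inside that window.

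**3. Expected relapses by then.** With a constant hazard (assumption), the expected number is 58 × (1 − S^(1.5/24)), where S is two-year RFS:

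- S = 0.64: 58 × 0.0275 = 1.6
- S = 0.70 (predecessor result, 14.2): 58 × 0.0220 = 1.3
- S = 0.80: 58 × 0.0139 = 0.8

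These are relapses at all sites. The marrow share is not given.

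**4. Simulation with no true association.** There were 58 patients, exponential relapse times, censoring at 24 months, a two-sided 5% log-rank test (14.4 states no level) and 3,000 runs per cell. Relapses up to 1.5 months are recorded at the marrow visit. Those in marrow are set PCR-positive; everyone else is PCR-positive at random with the stated probability. Percentage of trials rejecting:

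| Early relapses in marrow | Two-year RFS | 15% PCR+ | 30% PCR+ | 50% PCR+ |
|---|---|---|---|---|
| All | 0.64 | 17.6 | 9.5 | 6.0 |
| All | 0.70 | 15.7 | 9.0 | 5.6 |
| All | 0.80 | 13.3 | 8.1 | 4.5 |
| Half | 0.64 | 10.5 | 7.5 | 5.1 |
| Half | 0.70 | 8.9 | 5.7 | 5.2 |
| Half | 0.80 | 7.8 | 6.0 | 5.7 |

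A repeat simulation moved the 50% column to 6–7% (all) and 4–5% (half), hence the slightly wider ranges quoted for it. Dropping patients who had relapsed by the marrow visit gave 4.0–5.6% in every cell.

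**5. Effect of a fixed number of same-specimen relapses** (two-year RFS 0.70; median hazard ratio in brackets):

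| Relapses on that marrow | 15% PCR+ | 30% PCR+ | 50% PCR+ |
|---|---|---|---|
| 0 | 4.7% (0.98) | 4.7% (1.00) | 4.3% (0.99) |
| 1 | 11.7% (1.48) | 6.4% (1.20) | 4.4% (1.11) |
| 2 | 21.9% (2.10) | 10.8% (1.43) | 6.6% (1.25) |

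The landmark version of these cells gives 4.3–5.6%, with median hazard ratios of 0.97 to 1.01.

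**The case against.** The strongest reply is that 14.4 is a two-sentence secondary section that leaves a detail open; it does not prescribe a wrong analysis. Section 12.1 fixes the origin for response duration, not RFS, and a log-rank or Cox analysis could start at the marrow date. This stands as a limit: a reader might infer that the plan explicitly runs RFS from first 3F8, and it does not. But no other clock is given, and 12.4 keeps every treated eligible patient in the analysis, so the section followed as written permits the problem.

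Stronger readings that the documents do not support:

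- **Early marrow relapses are PCR-positive by construction.** No RT-PCR cutoff is defined, and 14.4 does not say the result will be dichotomised. Positivity is very likely, not guaranteed, and relapses outside marrow need not be PCR-positive.
- **False-positive rates of a third to a half.** The simulation reaches these (32% and 47% at two-year RFS 0.64 and 15% PCR-positive) only with three or four marrow relapses at that one visit. Even with marrow at month 2 and RFS 0.64, about 2.1 relapses are expected at all sites. If half are in marrow, the binomial chance of three or more is about 9%, and of four or more about 2%.
- **RT-PCR steers treatment in this trial.** Section 3.8 is conditional and looks to future programs. No treatment rule here uses the result.
- **The predictor is contradictory or must be baseline-adjusted.** The summary does say "we will test the hypothesis that early bone marrow response has prognostic importance", whereas the objective names content after treatment. The formal objective is specific enough to govern. Adjusting for the pretreatment level asks a different question, about incremental value, and is a preference.

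**Conclusion.** The concern holds as a gap in a secondary analysis that can bias the test of the stated hypothesis. The mechanism follows from the documents; its size does not.

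Under the assumptions above, a nominal 5% test rejects in about 13–18% / 8–10% / 5–7% of trials at 15% / 30% / 50% PCR-positive if all early relapses are in marrow. If half are, it rejects in about 8–11% / 6–8% / 4–6%. The landmark analysis stays at 4–6%. The inflation is therefore material when PCR positivity is uncommon, and close to nil when about half the patients are positive or no marrow relapse appears at that visit.

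The PCR-positive share, marrow share, constant hazard, marrow date and test level are all assumptions. The simulation uses a binary marker and does not evaluate a continuous transcript level. Patients treated from A(8) are evaluable for toxicity only (14.0), so the number analysed may be below 58, in which case each early relapse would weigh more.

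**What to change.** Amend 14.4 so that, for the marker analyses:

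- RFS starts at the date of the post-cycle-2 marrow.
- Only patients with no progression documented on or before that evaluation are included. This covers the marrow specimen itself and any imaging already done. Section 10.7 schedules only marrow studies at that point, and no new imaging is required.
- The predictor is the post-cycle-2 RT-PCR content named in the secondary objective.
- Relapses at or before the landmark are reported separately, with their RT-PCR and histology readings where available. This also covers patients who progress before giving a marker value.

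One consequence should be stated: if a positive post-cycle-2 histology counts as relapse, nobody in the landmark set has one, so that reading cannot be tested against later RFS and should only be described.

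The cost is wording, with no new data. The few patients who relapse by the landmark leave this secondary analysis but stay in the primary endpoint. The two-stage design does not change.
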